7.1.2.3 Tumor Tissue Collection and Correlative Studies Blood Sampling

For patients participating in the Penn Melanoma Tissue Collection Program (UPCC #08607, IRB #703001), blood samples will be collected, processed, and stored according to the program's standard operating procedure. Currently, this includes drawing less than 65 mL of blood according to the following schedule (after initiation of pembrolizumab): weeks 0, 3, 6, 9, 12, 15, and at 1 year. For the purposes of this study, patients will have an additional sample of blood drawn at approximately 1 week after starting pembrolizumab; this sample will also be collected, processed, and stored according to the Penn Melanoma Tissue Collection Program standard operating procedure. If patients have not consented to participate in the Penn Melanoma Tissue Collection Program, then no blood samples will be drawn for the purposes of this study. Analysis of blood samples will include, but is not limited to, analysis of serum cytokines, chemokines, and T cell markers; proposed cytokines and chemokines are listed in Table 1, and proposed T cell markers are listed in Table 2. This data will be correlated to patient response as well as changes in tumor FDG uptake. Some of these studies will be performed upon receipt of additional funding. There may be patients for which some or all of these blood draws are not possible, in this case it will be documented in the CRF and the blood draws may be omitted and it will not be considered a protocol deviation. Experimental pathology results will not be reported to the participant and will have no impact on the treatment decisions made by the treating physician.

Patients may undergo tumor biopsy as part of their clinical care prior to initiation of pembrolizumab. For patients participating in the Penn Melanoma Tissue Collection Program, these pre-therapy tissue samples will be collected, processed, and stored according to the program's standard operating procedure. For the purposes of this study, patients will have a post-therapy tumor biopsy which will be scheduled within 7 days after the 1st Post-therapy

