FDG PET/CT; this tissue will also be collected, processed, and stored according to the Penn Melanoma Tissue Collection Program standard operating procedure. If patients have not consented to participate in the Penn Melanoma Tissue Collection Program, then no tumor biopsies will be performed for the purposes of this study. The biopsy techniques preferred for this study include core biopsies or surgical biopsies. The same biopsy techniques should be used as routinely used for a given tumor lesion/location. When possible, the post-therapy tumor biopsy should target the same lesion that was biopsied pre-therapy; if the original lesion cannot be biopsied, then a lesion with a significant change in FDG activity should be targeted for biopsy. Analysis of tissue samples will include, but is not limited to, analysis of tumor-infiltrating lymphocytes (TILs), macrophages, and other myeloid subsets; changes in tumor cells will also be evaluated, and the fraction of necrotic cells will be calculated. TILs will be analyzed using multiparameter flow cytometry; proposed phenotypic markers are listed in Table 2. This data will be correlated to patient response as well as changes in tumor FDG uptake. Some of these studies will be performed upon receipt of additional funding. There may be patients for which a pre- or post- therapy tumor biopsy is not performed; those cases will be documented in the CRF and will not be considered a protocol deviation. In some cases tissue may be collected outside of the 7 day window following the 1st Post-therapy FDG PET/CT; this will not be considered a protocol deviation. Experimental pathology results will not be reported to the participant and will have no impact on the treatment decisions made by the treating physician.

For patients participating in the Penn Melanoma Tissue Collection Program, we will follow the standard operating procedure regarding archival tissue access for patients undergoing a biopsy or surgery on melanoma or other skin cancer for diagnosing, treating or research purposes, but for which there is no applicable left over fresh tissue, or patients who had a biopsy or surgical procedure done on melanoma or other skin cancer for diagnosing, treating or research purposes at the University of Pennsylvania Health System (UPHS) or at an institution outside of UPHS. If patients have not consented to participate in the Penn Melanoma Tissue Collection Program, then no archival tissue will be requested.

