8.0 STATISTICAL CONSIDERATIONS

8.1 Design:

This is a pilot correlative study for patients with metastatic melanoma receiving pembrolizumab on a standard regimen. The intent of this study is to evaluate FDG PET/CT as an early measure of response to immunotherapy. Tumor FDG uptake will be measured at baseline and at 3 and >10 weeks after initiation of pembrolizumab. 30 evaluable patients will be enrolled; evaluable implies that the patient had baseline and week 3 FDG PET/CT scans. This study will also include serum and tissue sampling for immune biomarkers.

8.2 Objectives:

The primary objectives are to:

1. Determine the distribution of changes from baseline in tumor FDG uptake on PET/CT at 3 weeks and >10 weeks after initiation of pembrolizumab.
2. Test for the association between change in tumor FDG uptake on PET/CT at 3 weeks and objective response (RECIST).

The secondary objectives are to:

1. Based on change in FDG uptake at 3 weeks, determine which patients have FDG “flare.”
2. Test for the association between FDG flare (yes/no) and objective response.
3. Test for the association between FDG flare and progression-free and overall survival.
4. Test for correlation between change in FDG uptake and levels of immune biomarkers in serum and tissue.
5. Test for association between changes in immune biomarkers in serum and tissue with objective response, progression-free survival, and overall survival.

8.3 Endpoints:

1. Objective response is defined by RECIST. The clinical evaluation takes place at 3 months per standard pembrolizumab regimens. Patients will be categorized as responders (complete response or partial response) or nonresponders (stable disease or progressive disease).

2. The maximum standardized uptake value (SUVmax) will be analyzed for all tumor sites. Immune-related tissues will be analyzed with SUVmax and SUVmean.
3. Studies have shown that the baseline test/re-test variability is 15-20%. Thus, FDG “flare” will likely be defined by >20% increase in tumor FDG uptake at 3 weeks. This definition may be modified for the observed distribution of changes in tumor FDG uptake on our study.
4. Progression-free and overall survival are defined in Section 4.1.2.
5. Immune biomarkers (see Section 7.1.2.3).

8.4 Plans for Data Analysis:

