This is a pilot correlative study of FDG PET/CT imaging to evaluate early response to immunotherapy. We will first begin with a descriptive analysis. For continuous variables, we will generate graphs and descriptive statistics (e.g., means, standard deviations, medians and inter-quartile range). Categorical variables will be described by frequencies, proportions and 95% exact confidence intervals. Change in tumor FDG uptake will be closely examined. It is likely that change in tumor SUVmax >20% will be classified as a FDG “flare” and the number of patients with a flare will be computed.

Next, associations between change in tumor FDG uptake with clinical outcomes will be conducted. Change in tumor FDG uptake at 3 weeks will be compared between responders and nonresponders by a two sample t-test. Also, objective response rates will be compared between patients with or without FDG “flare” by Fisher’s exact test.

PFS and OS will be estimated by the method of Kaplan and Meier. Median values and 95% confidence intervals will be calculated. PFS and OS will be compared between patients with or without FDG “flare” by the log rank test. Cox regression may be used to assess the effect of continuously scaled measurements of FDG change. For all survival analyses, a landmark analysis will be performed. Here, PFS or OS are defined from a landmark, which is 3 weeks after initiation of pembrolizumab. The landmark method is necessary because the change in tumor FDG uptake is known at 3 weeks. Serum and tissue biomarkers will be correlated with change tumor FDG uptake, using Pearson correlation or Spearman’s correlation, as appropriate. Within-patient pre-/post-treatment changes in biomarkers will be evaluated by paired Student’s t-test or Wilcoxon signed ranks test, as appropriate. We will test for an association between post-/pre-treatment fold change in immune biomarkers in serum and tissue and objective response, progression-free survival, and overall survival using logistic regression (for response) and Cox regression (for time-to-event outcomes) using landmark survival analysis.

8.5 Sample Size Justification:

The target is 30 evaluable patients, which may require up to 35 enrolled patients. Based on our clinical experience, we assume a 50% objective response rate, thus there will be 15

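### Section 8.4 tests biomarker fold change against response by logistic regression with no named test or small-sample method, which matters mainly if the paired tissue subset is well below 30 patients

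*Combined protocol and SAP*

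**What the plan says.** Secondary objective 5 in Section 8.2 is to "Test for association between changes in immune biomarkers in serum and tissue with objective response, progression-free survival, and overall survival". Section 8.4 carries this out by relating "post-/pre-treatment fold change in immune biomarkers in serum and tissue and objective response" and the survival endpoints, "using logistic regression (for response) and Cox regression (for time-to-event outcomes". For the response part it does not say:

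- whether the p-value is Wald, likelihood-ratio, score, exact or penalised;
- what the significance level and sidedness are;
- whether fold change is analysed on the log scale;
- what happens if a marker separates the two groups.

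For FDG change, the same section compares responders with nonresponders by a two-sample t-test. It uses Fisher's exact test for flare against response.

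On numbers, Section 8.5 states: "The target is 30 evaluable patients, which may require up to 35 enrolled patients". It continues: "we assume a 50% objective response rate, thus there will be 15" responders and 15 nonresponders. Section 8.1 adds that "evaluable implies that the patient had baseline and week 3 FDG PET/CT scans", so neither blood nor tissue is needed to be evaluable. Section 7.1.2.3 says of tissue: "There may be patients for which a pre- or post- therapy tumor biopsy is not performed". It says of blood: "There may be patients for which some or all of these blood draws are not possible". A study biopsy also requires consent to a separate tissue collection programme.

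**The concern.** A paired tissue fold change exists only where both a pre-treatment and a post-treatment sample exist. The pre-treatment biopsy is taken only as part of clinical care, and either biopsy may be absent. The tissue analysis will therefore probably have fewer than 30 patients, possibly many fewer.

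The two usual maximum-likelihood tests fail in different directions in samples of that size. The Wald test becomes very conservative, and once a marker is strong enough to separate the groups it stops rejecting. The likelihood-ratio test rejects too often when there is no effect. With neither named, the result for a given marker can depend on software defaults, or on a choice made after the data are seen. At stake is whether the tissue part of objective 5 can detect a strong marker, and what error rate applies to a positive result.

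**Working it through.** **The plan's own figure.** Section 8.5 gives 84% power for FDG change: 15 v 15, 1.0 SD, one-sided 5% t-test. Noncentrality = 1.0 × √(15 × 15 / 30) = √7.5 = 2.74 on 28 degrees of freedom, which gives 84.8%. The figure reproduces. Two-sided, it is 75.3%. No power figure is given for the biomarker regressions.

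**Inputs.** From the documents: one fold-change covariate, binary response, 15/15 split, target of 30. Assumed, because the documents are silent: two-sided 5%; log fold change normal with SD 1 in each group; a shift of d SD between groups; near-equal split; paired subsets of 20, 15 and 10.

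**Formulae.** The model is logit P(response) = α + βx. The Wald statistic is z = β̂/SE(β̂). The likelihood-ratio statistic is 2(ℓ₁ − ℓ₀), referred to chi-square on 1 df. Under complete separation β̂ diverges and its standard error grows faster, so z tends to 0 and the Wald p-value tends to 1. In the same sample ℓ₁ tends to 0, so with an equal split the likelihood-ratio statistic tends to −2ℓ₀ = 2n ln 2. For n = 10 that is 2 × 10 × 0.693 = 13.9, or p of about 0.0002. The same data can thus give opposite answers.

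**Type I error** (simulated, nominal 5%; 20,000 or more data sets per cell, Monte Carlo SE at most about 0.15 points):

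| n | Wald | Likelihood ratio | Firth penalised LR |
|---|---|---|---|
| 30 | 3.5% | 5.9% | 4.4% |
| 20 | 2.3% | 6.4% | 4.6% |
| 15 | 0.8% | 6.9% | 4.3% |
| 10 | 0.0% | 8.7% | 4.1% |

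The t-test on log fold change is at 4.6 to 5.0%. Smaller runs put the likelihood-ratio figure at n = 10 nearer 8%.

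**Power** (rounded; separate runs agree within about 2 points):

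| n | d (SD) | Wald | Likelihood ratio | t-test | Firth |
|---|---|---|---|---|---|
| 30 | 1.0 | 70% | 78% | 75% | 75% |
| 30 | 2.0 | 94% | 100% | 100% | 100% |
| 30 | 3.0 | 49% | 100% | 100% | 100% |
| 20 | 2.0 | 68% | 99% | 99% | 99% |
| 15 | 1.5 | 20% | 82% | 76% | 73% |
| 15 | 2.0 | 22% | 97% | 94% | 93% |
| 10 | 2.0 | 0% | 87% | 79% | 75% |

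The likelihood-ratio power is partly bought with its excess type I error.

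**Size of the Wald loss at 30.** At 1.0 SD: 75.1 − 69.9 = 5.2 points against the t-test. At 1.5 SD: 98.3 − 96.0 = 2.3 points against the likelihood-ratio test. At 2.0 SD: 99.96 − 93.5 = 6.5 points against Firth. Wald power then falls to 76% at 2.5 SD and 49% at 3 SD.

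**Separation.** At 30 patients it occurs in about 2% of samples at 2.0 SD and 28.5% at 3 SD. At 15 pairs it occurs in about 6% at 1.5 SD, 19% at 2.0 SD and 61% at 3 SD. On log fold change, the Wald p-value exceeded 0.05 in every separated sample.

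**Scale.** If raw fold change is entered and is lognormal (log SD 1), likelihood-ratio type I error is 7.1% at 30 and 9.6% at 10. Wald power at 30 patients and 1.0 SD drops from 70% to 42%. The mild result at 30 therefore depends on taking logs.

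**The case against.** **The plan names neither faulty test.** This is correct. Wald, likelihood-ratio, exact and penalised tests all fit its wording, and Firth's method is itself logistic regression. A reader might infer that the plan commits to the Wald test, or that both failures would occur together. The documents support neither: a single analysis would have one fault or the other. The defect is an unspecified test with no small-sample safeguard.

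**The worst figures rest on assumed pair counts.** This also stands. No section gives 10, 15 or 20 pairs. Section 2.1 says almost all melanoma patients in the health system have consented to the collection programme, so serum numbers may be near 30. Archival tissue may supply some missing pre-treatment samples, though not a missing post-treatment one. Up to 35 patients may enrol, and nothing limits biomarker analyses to evaluable patients; at 35 the likelihood-ratio type I error is still 5.8%.

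**The strongest markers are not generally the ones missed.** A reader might infer that they are. At 30 patients the Wald test misses a 1.0 SD marker about 30% of the time and a 2.0 SD marker about 6%. At 15 pairs its power rises from about 10% at 1.0 SD to 22–24% at 2.0 SD. Power falls with increasing strength only beyond about 1.5 to 2 SD, and materially at 30 patients only from about 2.5 SD.

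**Dropping logistic regression would have a cost.** Secondary hypothesis 4 in Section 3.2 concerns the value biomarkers add to FDG imaging in predicting response. A two-sample test cannot address that, and logistic regression is the only response model in 8.4.

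**A separating marker would be visible** in the graphs that 8.4 plans first. That lowers the risk of a strong marker being overlooked, but leaves the reported p-value and interval unusable.

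**Conclusion.** The point holds as a limited one. Section 8.4 leaves the response test for biomarkers unspecified, and neither usual maximum-likelihood test is satisfactory in a small paired subset. Wald power is about 20% where a t-test has 76% (15 pairs, 1.5 SD), about 68% against 99% at 20 pairs and 2.0 SD, and essentially zero at 10 pairs. Likelihood-ratio type I error is about 7% at 15 pairs and 8 to 9% at 10. At a full 30 patients on the log scale, the Wald loss is about 2 to 6 points for 1.0 to 2.0 SD, and the likelihood-ratio excess is about 1 point.

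These figures assume normal log fold change, a near-equal response split, two-sided 5% tests and pair counts that the documents do not give. The analyses are secondary in a pilot study. The primary t-test on FDG change and its 84% power are not affected. The change is worth making because it is cheap and the better methods are clear.

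**What to change.** In Section 8.4:

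- Keep logistic regression for response, but specify log fold change as the covariate, and Firth's penalised likelihood with penalised likelihood-ratio p-values and profile-likelihood intervals. This stays finite under separation and keeps a model that can combine biomarkers with FDG data for secondary hypothesis 4.
- For the single-marker comparison of responders with nonresponders, take the p-value from a two-sample t-test or exact Wilcoxon test on log fold change, in line with the t-test already planned for FDG change.
- State the significance level and sidedness for these tests, and report the number of paired samples behind each result.

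The cost is a few sentences of analysis plan, with no new data or patients. The statistical price is small. In these simulations the Firth test is slightly conservative (about 4% at 10 to 15 pairs) and somewhat less powerful than the t-test there (75% v 79% at 10 pairs and 2.0 SD). Its odds ratios are also shrunk slightly.

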3.0 OBJECTIVES & HYPOTHESES

3.1 Primary Objectives & Hypotheses

(1) **Objective:** To determine the distribution of changes from baseline in tumor FDG uptake on PET/CT at 3 weeks and >10 weeks after initiation of pembrolizumab.

Hypothesis: None, descriptive statistics.

(2) **Objective:** To evaluate the ability of FDG PET/CT to serve as an early measure of objective response to therapy in patients with melanoma on pembrolizumab.

Hypothesis: Melanoma metastases demonstrate changes in FDG uptake on a 3 week PET/CT scan that are associated with objective response to pembrolizumab.

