It has recently been recognized that immune activation results in a similar cellular metabolic switch from oxidative phosphorylation to aerobic glycolysis. This occurs with both the innate and adaptive immune activation. For example, when activated using TLR ligands or pro-inflammatory cytokines, neutrophils, dendritic cells, and macrophages have been demonstrated to switch their metabolism from oxidative phosphorylation to aerobic glycolysis.⁵ Similarly, following TCR stimulation, lymphocytes increase glucose utilization by several orders of magnitude and switch glucose metabolism from oxidative phosphorylation to aerobic glycolysis.^{6,7} Interestingly anti-inflammatory subpopulations of both the innate and adaptive immune system, such as M2 macrophages, regulatory T cells and quiescent memory T cells, demonstrate a predominant use of oxidative phosphorylation rather than aerobic glycolysis as opposed to their inflammatory counterparts such as activated macrophages and T-helper 17 cells.⁸

The upregulation of aerobic glycolysis in immune activation is readily visualized with FDG PET/CT imaging. Inflammatory conditions such as infection, rheumatoid arthritis and sarcoidosis yield intense avidity for FDG that compares with or exceeds that of most malignancies.^{9,10} In fact, a significant limitation to the use of FDG PET/CT in cancer restaging has been interference of the tumor FDG signal by post-therapeutic inflammatory tissues including surgical changes, talc pleurodesis, and radiation therapy.¹¹

In this study we propose utilizing FDG PET/CT to assess the immunotherapy response by detecting the superimposed increased metabolism within the tumor presented by a therapy-induced infiltrating population of glucose avid activated immune cells. Of note, a flare

phenomenon has been described in several cancer types following therapy; in patients with breast cancer on endocrine therapy, a clinical flare response was identified in 4 of 17 responders and 1 of 34 nonresponders, and an FDG PET flare response was seen in 15 of 17 responders and none of the 34 nonresponders.¹² These results suggest that FDG PET is more sensitive and specific for detecting a flare response compared to clinical criteria, and the results also suggest that a flare response is predictive of response to therapy.

FDG PET/CT studies are typically performed at approximately 12 weeks following the initiation of

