pembrolizumab, and the probability of seeing a flare response on these clinical studies is very low; this is supported by data presented at ASCO in 2014, in which 3.6% of patients with melanoma

demonstrated a flare response on imaging ($\geq 25\%$ increase in tumor burden) at 12 weeks. We propose looking for a flare response at about 3 weeks following the start of immunotherapy. The choice of this time point is considered appropriate for the activation and expansion of immune cells and is supported by data on pembrolizumab in non-small cell lung cancer, which revealed that circulating cytotoxic T cells specific to tumor neoantigens peak at around 3 weeks from the initiation of therapy (Figure 1).¹³ Additional data on pembrolizumab in multiple other tumor types also found that activated cytotoxic T cells peak at around 3 weeks.¹⁴

[figure not shown]

Figure 1: Neoantigen-specific T cell response to pembrolizumab in non-small cell lung cancer. In a study by Rizvi *et al*, the magnitude of the neoantigen (HERC1 P3278S) reactive CD8+ T cell response was measured in peripheral blood of patients with non-small cell lung cancer receiving pembrolizumab by determining proportion of CD8+ T cell population in serially collected autologous peripheral blood lymphocytes recognizing the HERC1 P3278S neoantigen (ASNASSAAK) before and during pembrolizumab treatment. In this study the neoantigen specific T cells begin to peak at day 21 of anti-PD1 therapy. (Nayer A. Rizvi *et al*. Science 2015;348:124-128.)

No significant change is expected in the tumor's inherent basal glycolytic activity over the short interval between the baseline FDG PET/CT and the 3 week PET/CT. Therefore we hypothesize that the flare response will be able to be visualized with FDG PET/CT by detection of a superimposed burst of tumoral glycolytic activity resulting from immunotherapy induced immune infiltration. If successful, this study will help to determine the ideal time point for visualization of the flare response, test the potential for the flare response to serve as a biomarker for detecting an early response to therapy, and contribute to our understanding of pembrolizumab's mechanism of action.

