responders and 15 nonresponders. A comparison of change in FDG SUV at 3 weeks between responders and nonresponders, will have 84% power to detect a 1.0SD difference in mean values, using 1-sided two sample t test at a 5% significance level. The 1-sided test is justified, since responders are expected to have greater changes in FDG SUV.

8.6 Study Duration:

This study will enroll 30 evaluable patients over 1 year.

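### Does a 1-sided primary t-test beside a non-directional hypothesis mean that the study's real power is 75% rather than 84%?

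*Combined protocol and SAP*

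**What the plan says.** The primary hypothesis in Section 3.1 is "Melanoma metastases demonstrate changes in FDG uptake on a 3 week PET/CT scan that are associated with objective response to pembrolizumab". The second primary objective in Section 8.2 likewise asks for a test of association, with no direction.

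Section 8.4 gives the method: "Change in tumor FDG uptake at 3 weeks will be compared between responders and nonresponders by a two sample t-test". It states neither side nor significance level.

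Section 8.5 supplies both. With an assumed 50% response rate in 30 evaluable patients, the comparison "will have 84% power to detect a 1.0SD difference in mean values, using 1-sided two sample t test at a 5% significance level". The reason given is "The 1-sided test is justified, since responders are expected to have greater changes in FDG SUV". No section describes the primary test as two-sided.

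**The concern.** A hypothesis of association is met by a difference in either direction, and the usual test for it is two-sided. Section 8.5 instead uses a 1-sided test, and its reason refers to greater changes without saying whether these are increases, decreases or absolute changes. The section that describes the analysis omits the side; the section that gives the side omits the sign.

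Three consequences could follow:

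- The quoted power could overstate the chance of success for the hypothesis in 3.1.
- If the tail were chosen after seeing the data, the 5% error rate would not hold.
- If the tail is upward, a smaller FDG change in responders could not be declared by the primary test, although it too might serve as an early measure of response.

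**Working it through.** **Inputs.** From Section 8.5: 15 responders, 15 nonresponders, a difference of 1.0 SD, 1-sided 5%. Equal SDs are assumed.

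**1. The plan's own figure.**
- Standard error in SD units: √(1/15 + 1/15) = 0.365.
- Degrees of freedom: 15 + 15 − 2 = 28.
- Noncentrality: 1.0 / 0.365 = 2.739.
- 1-sided 5% critical value: 1.701.
- Power = P(noncentral t > 1.701) = 84.8%.

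The stated 84% reproduces. The normal approximation gives 86.3%, so the t-based calculation is the one that matches.

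**2. The same design, two-sided.**

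| Test | Power at 1.0 SD |
|---|---|
| 1-sided 5% (Section 8.5) | 84.8% |
| Two-sided 5% | 75.3% |
| Two-sided 10% | 84.8% |

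The loss under two-sided 5% is 84.8 − 75.3 = 9.5 points, and 80% power would then need 1.06 SD. The 75% is therefore not a property of the hypothesis in 3.1, which gives neither side nor level. It appears only when a two-sided 5% level is added.

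**3. Where the choice changes the conclusion.** The observed difference needed for significance is 1.701 × 0.365 = 0.62 SD 1-sided, and 2.048 × 0.365 = 0.75 SD two-sided at 5%. Only a result between these, in the expected direction, would be read differently.

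**4. Tail left open.** If the tail were picked after the data, the error rate would be P(|t| > 1.701) = 10%. This depends on whether the documents really leave the tail open, so the relevant statements are set side by side:

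- The trial summary (1.0) names the study after the flare response.
- Section 3.2 defines flare as an early rise in tumor uptake.
- Section 4.1 expects the tumor's own glycolysis to stay about level between the two scans. It looks for flare by "detection of a superimposed burst of tumoral glycolytic activity resulting from immunotherapy induced immune infiltration".
- Section 4.1 cites a breast cancer study in which "an FDG PET flare response was seen in 15 of 17 responders and none of the 34 nonresponders".
- Sections 7.1.5 and 8.3 set flare at an increase of more than 20%, in SUVmax and in tumor uptake respectively.

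The only change that the rationale predicts is an increase, and it predicts it in responders. Read with 8.5, the tail is a larger signed increase in responders.

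**5. The untested tail.** With an upward tail, a true difference of −0.5 SD is declared with probability 0.14% (26% under two-sided 5%), and −1.0 SD with probability 0.0008% (75%). Any 1-sided test behaves this way; the figures do not show a fault in this one.

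**6. Cost of switching.** Under two-sided 5%, 18 per group gives 83.0% and 19 per group gives 85.1%. Restoring at least 84% would need 2 × 19 = 38 evaluable patients, against a target of 30 and planned enrollment of up to 35.

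**The case for a change.** The best case for a change is that a tail inferred from background is not a prespecified tail. The protocol puts the word increase into the secondary flare objective and the flare definitions but leaves it out of the primary hypothesis, so the primary aim could be deliberately wider. Section 8.4 even describes flare at one point as a change above 20%, without a sign, and 8.3 allows the flare cut-off to be revised after the distribution is seen. A formal power claim should be reproducible from the analysis section alone, and either wording repair would cost no patients or procedures.

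Part of this stands. Section 8.4 is silent on side and level, and no sentence states the sign as the tail of the primary test. But silence in 8.4 does not contradict 8.5: general wording in 3.1 and 8.2 is followed by one specific statement, with its reason. The adjustable cut-off concerns the yes/no flare analyses; the primary t-test uses the continuous change and needs no cut-off. A smaller change in responders would still be visible, because the first primary objective is descriptive and 8.4 begins with graphs and summary statistics. Nor would the choice of side be hidden from a reader: for a result in the expected direction, the two-sided p-value is twice the 1-sided one.

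**Conclusion.** The concern does not call for a change. The 84% is right for the 1-sided 5% test that Section 8.5 openly declares. The 75.3% is right only for a two-sided 5% test, which the documents never specify. The 10% error rate needs a reading in which the flare rationale is set aside and the tail is chosen afterwards, and nothing in the plan suggests that.

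The unstated sign and the omission in 8.4 are missing detail. An analyst would take side and level from 8.5 and direction from 3.2, 4.1 and 8.3, and would arrive at a 1-sided 5% test of a greater SUVmax increase in responders, with power unchanged. Replacing that test with a two-sided one would give up about 9.5 points of power to cover a direction that the rationale does not expect. In a pilot of 30 evaluable patients, either choice is defensible.

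The power figures rest on the plan's 15/15 split, equal SDs and a true difference of 1.0 SD.
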